### **5.3.3. Long-Term Extension Period**

Subjects who received aducanumab in the placebo-controlled period and who enter the LTE period will continue to receive the same dose of aducanumab that they were on at the end of the placebo-controlled period. Subjects who receive placebo during the placebo-controlled period and who enter the LTE period will be assigned to 1 of 2 treatment groups, based upon their ApoE  $\epsilon$ 4 carrier status, in a 1:1 ratio (aducanumab low dose: aducanumab high dose). Subjects will be dosed using the same regimen described for the placebo-controlled period (see [Table 7](#) and [Figure 1](#)).

Any modifications to the dosing scheme (i.e. termination of high dose groups and replacement of titration with fixed dosing, as described in [Section 5.3.2](#)) will also be implemented in the LTE period.

CONFIDENTIAL

The information contained herein may not be used, disclosed, or published without the written consent of Biogen MA Inc.

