The total duration of study participation for each subject participating in the placebo-controlled period and the LTE period will be up to approximately 206 weeks, including a series of Screening visits within 8 weeks before administration of the first dose, a 76-week placebo-controlled treatment period, a 4-week FU period, a 100-week aducanumab dose-blind treatment period, and a safety FU period of approximately 18 weeks after the final dose. The FU period of 18 weeks is based on an estimated mean elimination half-life in humans of 16 to 24 days (mean approximately 20 days, based on results from the single ascending dose study [Study 221AD101]) and anticipated brain concentrations of aducanumab of less than one-third the  $EC_{50}$  (inhibitory concentration at 50% of the maximum observed biologic effect) for binding fibrillar amyloid at 8 weeks after the last dose.

During the placebo-controlled period, ApoE  $\epsilon$ 4 carriers will receive placebo, aducanumab 3 mg/kg, or aducanumab 6 mg/kg whereas ApoE  $\epsilon$ 4 non-carriers will receive placebo, aducanumab 6 mg/kg, or aducanumab 10 mg/kg. Aducanumab will be titrated for up to 6 doses prior to reaching the target dose as shown in [Table 7](#) and [Figure 1](#). Subjects who received

CONFIDENTIAL

The information contained herein may not be used, disclosed, or published without the written consent of Biogen MA Inc.

aducanumab in the placebo-controlled period and who enter the LTE period will receive the same dose of aducanumab that they received at the end of the placebo-controlled period (up to 6 mg/kg and 10 mg/kg in ApoE  $\epsilon$ 4 carriers and non-carriers, respectively). Subjects who received placebo during the placebo-controlled period and who enter the LTE period will be assigned to treatment based upon their ApoE  $\epsilon$ 4 carrier status in a 1:1 ratio (aducanumab low dose: aducanumab high dose); aducanumab will be titrated for up to 6 doses prior to reaching the target dose following the same schedule described for the placebo-controlled period.

See Section 5.3.2 for details of dosing scheme modification.

Individual dose adjustments may also be implemented to subjects who develop ARIA. See Section 7.2.1.

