## **7.2. Study Specifics**

### **7.2.1. Dose Suspension, Modification, or Termination for ARIA Events**

#### *Discontinuation of Dosing for a Given Subject*

The central MRI reading center will report incident cases of ARIA-E and ARIA-H to both the Sponsor and the PI within a specified time after observing the finding on MRI per the imaging manual procedures. All cases of ARIA will be reviewed by the Sponsor and the PI; decisions on dosing continuation, interruption, or discontinuation will be based on clinical symptoms, and the MRI information provided by the central reader. IDMC notification rules will be outlined in the IDMC charter. Guidelines on the management and disposition of ARIA-E and ARIA-H cases (including the criteria to be met for the continuation, suspension/resumption, permanent discontinuation of dosing due to ARIA, resumption of dosing after dose suspension due to ARIA [including rules for titrating up to the assigned dose], and management of recurrent ARIA) are provided in the following subsections. Dosing may also be terminated at the discretion of the Sponsor for medical reasons. See Section 10.1 for the full list of criteria for discontinuing study treatment.

CONFIDENTIAL

The information contained herein may not be used, disclosed, or published without the written consent of Biogen MA Inc.

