##### 7.2.1.6.2. Dosing Upon Resumption of Study Treatment

Subjects who suspend treatment due to ARIA for the first time may resume treatment at the same dose if they meet the criteria as described in Sections 7.2.1.1 to 7.2.1.5. Subjects who suspend and then resume dosing after having already reached their assigned top dose level are to continue dosing at that dose level. However, if dosing is suspended during the dose titration period, the

CONFIDENTIAL

The information contained herein may not be used, disclosed, or published without the written consent of  
Biogen MA Inc.

subject (1) must receive at least 2 doses at the restart dose before titrating up to the next dose level and (2) must complete at least the required number of doses at that dose level per their assigned dosing regimen, as outlined in Table 11.

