**7.2.1.7. Management After Recurrent ARIA (Dosing and MRI)**

If the subject has a second occurrence of ARIA (i.e., a second occurrence of ARIA-E or of ARIA-H, or ARIA-E and ARIA-H) that requires dose suspension, after the ARIA-E resolves or stabilizes, the subject is to resume dosing at the next lower dose and is to receive 2 doses at that

CONFIDENTIAL

The information contained herein may not be used, disclosed, or published without the written consent of Biogen MA Inc.

dose level (i.e., the restart dose) before titrating up to the next higher dose. Once dosing has resumed, the guidelines outlined in Table 11 apply, unless the subject has reduced from 1 mg/kg to placebo. In this case, the subject will remain on placebo for the duration of the placebo-controlled portion of the study. If a subject resumes treatment after ARIA, an MRI and MOCA will be performed as well as biomarker and PK sample collection 2 weeks ( $\pm 3$  days) after the second administration of the restarted dose, and 2 weeks ( $\pm 3$  days) after the second administration of each increase in dose unless the subject has a scheduled MRI during this period. MRIs will otherwise be performed as indicated in the Schedules of Events (Section 4.2).

If the subject experiences a third episode of ARIA that requires dose suspension, the subject must discontinue study treatment. Subjects who discontinue treatment are to remain in the study and continue all protocol-required tests and assessments.

Subjects who develop ARIA during the placebo-controlled period but continue or resume treatment at an active dose are eligible to enter the LTE period and will receive the lowest dose that they have tolerated during the placebo-controlled period. A subject who is switched to placebo but remains in the study may be titrated to aducanumab 1 mg/kg during the LTE period.

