### **8.3. Inclusion Criteria for Long-Term Extension Period**

To be eligible to participate in the LTE period, subjects must meet the following eligibility criteria at Week 78:

1. Subject must have completed the placebo-controlled period of the study including the Week 78 Visit. Subject must have taken at least 14 doses and not have missed more than 4 consecutive doses. Subjects who do not meet these criteria can enter the LTE period only with Sponsor's approval.
2. MMSE score >15 at the Week 78 Visit.
3. The subject (or the subject's legally authorized representative) has the ability to understand the purpose and risks of the study and provide signed and dated informed consent (or assent) and authorization to use confidential health information in accordance with national and local subject privacy regulations.
4. Female subjects of childbearing potential and male subjects must practice highly effective contraception during the study and for 24 weeks after their last dose of study treatment.
5. Apart from a clinical diagnosis of AD, the subject must be in good health as determined by the Investigator, based on medical history.
6. Must have the ability to comply with procedures for protocol-related tests.
7. Has one informant/care partner who, in the Investigator's judgment, has frequent and sufficient contact with the subject as to be able to provide accurate information about the subject's cognitive and functional abilities. The informant/care partner must minimally

CONFIDENTIAL

The information contained herein may not be used, disclosed, or published without the written consent of  
Biogen MA Inc.

be available by phone to provide information to the Investigator and study staff about the subject and agrees to attend in person clinic visits that require partner input for scale completion. An informant/care partner should be available for the duration of the study, and the use of the same informant/care partner for the duration of the study is encouraged.

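### In protocol v3.0 (same in v2.0), the extension dose that 7.2.1.7 sets for subjects with ARIA disagrees with 5.3.3 and 7.1 and, taken literally, is the 1 mg/kg starting dose

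*Protocol*

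**What the plan says.** Section numbers refer to protocol v3.0 unless stated otherwise.

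- **General rule.** Under 5.3.3, aducanumab subjects entering the extension "will continue to receive the same dose of aducanumab that they were on at the end of the placebo-controlled period". Section 7.1 repeats this: they "will receive the same dose of aducanumab that they received at the end of the placebo-controlled period".
- **Pointer in 7.1.** The same section adds: "Individual dose adjustments may also be implemented to subjects who develop ARIA", and refers to 7.2.1. It says nothing there about the extension dose. Section 5.3.3 has no such pointer.
- **ARIA rule.** Section 7.2.1.7 covers subjects with ARIA who continued or resumed on an active dose. It makes them eligible for the extension and says they "will receive the lowest dose that they have tolerated during the placebo-controlled period".
- **Re-titration.** Section 7.2.1 announces guidance on "resumption of dosing after dose suspension due to ARIA [including rules for titrating up to the assigned dose". After a first suspension, dosing resumes at the same level. If that happens during titration, 7.2.1.6.2 says the subject "must receive at least 2 doses at the restart dose before titrating up to the next dose level", and Table 11 gives the counts. After a second suspension, 7.2.1.7 drops the subject one level for 2 doses "before titrating up to the next higher dose".

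v2.0 has the same three dose statements (5.3.3, 7.1 and 7.2.2.6). The v4.0 contents list still shows 5.3.3, 7.1, 7.2.1.6, 7.2.1.7 and Table 11, but the available v4.0 text stops in the schedule tables before reaching them.

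**The concern.** Two rules set the extension dose for the same people, and they can give different answers. Following 7.2.1.7 as written also cancels the upward titration that 7.2.1.6.2, Table 11 and 7.2.1.7 itself prescribe: a subject who has returned to the assigned dose and tolerated it would be lowered again on entering the extension.

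This is a dosing instruction for up to 26 further infusions (7.3.2). Investigators stay blinded to dose in the extension (7.1, 9.3), so they cannot settle the ambiguity case by case. Section 16.2.2.6.2 presents extension results by the treatment group of the placebo-controlled period, so unintended step-downs would sit unmarked inside the active groups.

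**Working it through.** The plan states no figure on this point, so there is none to reproduce. The check compares the dose under 5.3.3 and 7.1 with the dose under 7.2.1.7, for each active regimen.

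**Inputs**
- Table 7: carrier low is 1 mg/kg for 2 doses, then 3. Carrier high and non-carrier low are 1 for 2 doses, 3 for 4 doses, then 6. Non-carrier high is 1, 3 and 6 for 2 doses each, then 10.
- Doses are 4 weeks apart, so dose k falls at Week 4(k − 1): dose 4 at Week 12, dose 6 at Week 20, dose 7 at Week 24, dose 20 at Week 76.
- Table 3: MRIs at Weeks 14, 22 and 30, among others.
- Resumption is allowed after at most 4 consecutive missed doses (7.2.1.1 to 7.2.1.3).
- Table 11: 2 doses at the restart level in the cases used here.

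**Reading A: lowest dose in the whole period, as the words stand.** All regimens start at 1 mg/kg, so the answer is 1 mg/kg for anyone who tolerated it. The ratios to the end dose are 3/1 = 3 (carrier low), 6/1 = 6 (carrier high, non-carrier low) and 10/1 = 10 (non-carrier high). This includes a subject with mild asymptomatic ARIA-E, or with 1 to 4 asymptomatic microhemorrhages, who never stopped full dosing (Tables 8 and 9).

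**Reading B: lowest dose after ARIA.** The text does not say this; it is one way to make sense of it. Take a first ARIA that suspends dosing, 1 to 4 missed doses, and no further event. Doses at the top level by Week 76 = (76 − first week at top)/4 + 1.

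| Regimen | MRI | Restart, mg/kg | First week at top (1 to 4 missed) | Doses at top | End dose / restart dose |
|---|---|---|---|---|---|
| Carrier high, non-carrier low | Week 14 | 3 | 28 to 40 | 13 to 10 | 6/3 = 2.0 |
| Carrier high, non-carrier low | Week 22 | 3 | 36 to 48 | 11 to 8 | 6/3 = 2.0 |
| Non-carrier high | Week 14 | 3 | 36 to 48 | 11 to 8 | 10/3 = 3.3 |
| Non-carrier high | Week 22 | 6 | 36 to 48 | 11 to 8 | 10/6 = 1.7 |

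Example, carrier high, Week 14, one missed dose: Week 16 is missed, 3 mg/kg is given at Weeks 20 and 24, and 6 mg/kg from Week 28, so (76 − 28)/4 + 1 = 13.

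Under reading B there is no difference for carrier low at these two MRIs, nor for any regimen with a first ARIA found from Week 30, because the restart dose is then already the top dose.

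A second ARIA at the top dose, followed by re-titration, gives 3/1 = 3.0 (carrier low), 6/3 = 2.0 (carrier high, non-carrier low) and 10/6 = 1.7 (non-carrier high).

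**Would such subjects qualify for the extension?** Section 8.3: "Subject must have taken at least 14 doses and not have missed more than 4 consecutive doses". After a first ARIA they have taken 20 − 4 = 16 to 20 − 1 = 19 doses. With ARIA at Weeks 30 and 54 and 1 to 3 missed doses each time, they have taken 20 − 6 = 14 to 20 − 2 = 18 doses, and are back at the top for 1 to 3 doses by Week 76. Both groups can enter.

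**The case against.** The strongest reply is that 7.1 refers ARIA cases to 7.2.1, so 7.2.1.7 is the specific rule and overrides the general one. Entering the extension at a lower dose after ARIA is cautious, can be applied, and errs toward less drug. That is a fair reading of how the sections rank, and for 7.1 it removes much of the conflict. It does not cover 5.3.3, which has no exception. Nor does it say which dose the phrase means: the literal answer is 1 mg/kg, and the section offers no other definition.

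A reader might infer that the sentence is a leftover. In v1.0 (7.2.1.1, 7.2.1.4) suspended subjects resumed one level down and no step up was described, so for a subject reduced from target the lowest post-ARIA dose was normally also the final dose. That history is plausible but unproven. v2.0 moved the sentence into the new section on recurrent ARIA, after the re-titration text, which fits a deliberate choice equally well. v1.0 was not clean either, since the sentence already covered subjects who simply continued at their current dose.

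How the dose is assigned in practice, through the IRT or pharmacy instructions, is not visible either, so inconsistent dosing at sites is a risk rather than something shown.

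**Conclusion.** The point holds as a minor finding for v2.0 and v3.0. The extension-dose rule for subjects with ARIA conflicts with 5.3.3, fits 7.1 only through a general pointer, and followed as written gives a dose unlikely to be intended.

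Three stronger inferences are not supported:

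- **That the problem measures 1.7- to 3.3-fold.** That range, and the absence of a difference for a single ARIA at the top dose, hold only under the post-ARIA reading, which is not in the text. The literal reading gives 3- to 10-fold and also covers subjects who were never reduced.
- **That the latest protocol carries the defect.** The v4.0 wording is not shown, and a surviving heading does not show that the sentence survived. v4.0 also raises the carrier high dose to 10 mg/kg, so the carrier-high figures above are for v3.0 only.
- **That the main result is at risk.** The Week 78 primary analysis is unaffected. Only dosing in the optional extension is involved, and the share of subjects is unknown because the protocol states no ARIA rate.

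**What to change.** Check 5.3.3, 7.1 and 7.2.1.7 in v4.0. If the sentence is still there, make one rule govern. Which one is a clinical decision.

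- **If no step-down is intended:** replace the phrase with *the dose the subject is receiving and tolerating when the placebo-controlled period ends*. This matches 5.3.3, 7.1 and the re-titration rules.
- **If a step-down after ARIA is intended:** name the level explicitly, for example *the dose at which treatment was restarted after the most recent ARIA that required suspension*, and exclude the initial titration doses. Then add *except as in 7.2.1.7* to 5.3.3 and 7.1.

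In either case, align the IRT dose assignment with the chosen rule. The cost is a short wording change, an IRT check and a notice to sites.

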### 7.2.2. Infusion Interruption

If any mild or moderate infusion-related reactions (e.g., headache, chills/rigors, and nausea/vomiting) occur during an infusion, the infusion should be slowed or interrupted and supportive treatment should be instituted at the discretion of the Investigator. After resolution of symptoms, if the infusion had been slowed, the original infusion rate may be resumed; if the infusion had been interrupted, the infusion may be restarted at a rate that does not exceed the original infusion rate. An infusion must be discontinued if not completed within 3 hours.

Refer to the Directions for Handling and Administration (DHA) for infusion rate information.

If a severe infusion-related reaction occurs during an infusion, or an allergic reaction such as urticaria or anaphylaxis occurs, the subject will be discontinued from study treatment but may remain in the study. The subject must be appropriately treated in accordance with local practice.

Severity of events is described in Section 15.2.3.

### 7.3. Overall Study Duration and Follow-Up

The study period will consist of screening, treatment, and FU.

The double-blind, placebo-controlled period of the study will consist of an 8-week screening period, a 76-week treatment period, and a safety FU period of 18 weeks after the final dose.

Subjects will have approximately 32 scheduled clinic visits during the placebo-controlled period, and up to 8 telephone safety FU contacts, as follows:

- Screening Visits no more than 60 days before the first dose of study treatment on Day 1 (visits will be conducted on multiple days). It is recommended that all screening procedures be completed within 60 days; however, the overall screening period may be extended up to 90 days in the event of logistical issues related to PET scans and subject to Sponsor approval.

CONFIDENTIAL

The information contained herein may not be used, disclosed, or published without the written consent of Biogen MA Inc.

- 20 outpatient dosing visits,
- 8 telephone safety FU contacts approximately 2 weeks after each of the first 8 doses.
- 3 visits for clinical assessments.
- [REDACTED]
- 3 visits (including Screening) for amyloid PET scan (in a subset of subjects).
- [REDACTED]
- 6 visits for brain MRI.
- 1 FU safety visit at Week 94 (only for subjects not entering the LTE period) or 18 weeks after last administration of study treatment for those subjects who withdraw from study.

Subjects who meet the LTE inclusion and exclusion criteria will be eligible to enter the LTE period. Subjects who enter the LTE period will have approximately 36 additional planned clinic visits, and up to 8 telephone safety FU contacts, as follows:

- 26 outpatient dosing visits.
- 8 telephone safety FU contacts approximately 2 weeks after each of the first 8 doses.
- 4 visits for clinical assessments.
- [REDACTED]
- 2 visits for amyloid PET scan (in a subset of subjects).
- [REDACTED]
- 7 visits for brain MRI.
- 1 FU safety visit.

Subjects who have a change in AD medication (other than study treatment) during the placebo-controlled or LTE period should have an unscheduled visit; all clinical assessments for the primary and secondary endpoints should be performed prior to the change in medication.

Subjects who experience ARIA during the placebo-controlled or LTE period should have unscheduled visits per the guidelines in Section 7.2.1.

### 7.3.1. Screening

During the Screening Visit, under a separate (optional) initial consent process, subjects can complete the neurocognitive scales (CDR, MMSE, and the Repeatable Battery for Assessment of Neuropsychological Status [RBANS]). This initial neurocognitive screening is intended to reduce the burden on subjects and sites by avoiding unnecessary testing if subjects do not meet key inclusion criteria. If the subject meets inclusion criteria for these 3 scales, then the full consent process must be completed prior to the administration of further screening assessments.

CONFIDENTIAL

The information contained herein may not be used, disclosed, or published without the written consent of Biogen MA Inc.

Subjects may also proceed directly to the full consent process, which would allow the administration of all screening assessments.

The neurocognitive assessments that have exclusion cut points (CDR, MMSE and RBANS) must be performed at Screening Visit 1. The ADAS-Cog 13 and ADCS-ADL-MCI will be performed at Screening Visit 2 within 20 days after Visit 1 and must NOT be performed on the same day as the CDR, MMSE and RBANS. The NPI-10 can be performed at any time during Screening as long as it is performed after the CDR (e.g., including at Screening Visit 1). All other cognitive assessments [REDACTED] may be performed at any time during Screening after eligibility is confirmed during Screening Visit 1. The MRI at Screening Visit 2 should be done only after the subject eligibility based on clinical and laboratory criteria is confirmed during Screening Visit 1. The PET scan at Screening Visit 3 should be completed only after the MRI inclusion criterion is met.

Subject eligibility for the study will be determined no more than 60 days prior to study entry. It is recommended that all screening procedures be completed within 60 days; however, the overall screening period may be extended up to 90 days in the event of logistical issues related to PET scans and subject to Sponsor approval.

Subjects who fail Screening will be permitted to be rescreened once at the Sponsor's discretion. Subjects who fail Screening due to PET, MMSE, CDR, hepatitis B or C results, or abnormal MRI findings will not be allowed to rescreen.

Subjects who fail Screening because allowed chronic medications have not been at stable doses for at least 4 weeks prior to Screening Visit 1 or whose use of AD medications has not been at stable doses for at least 8 weeks prior to Screening Visit 1 may return for rescreening after use of these medications has been stabilized for the required period.

### **7.3.2. Treatment**

Eligible subjects will report to the study site to receive study treatment every 4 weeks for 76 weeks (20 doses). All subjects who meet the LTE inclusion and exclusion criteria will be eligible to enter the LTE period and will receive study treatment every 4 weeks for an additional 100 weeks (26 doses), with the first dose administered approximately 4 weeks after the final dose in the placebo-controlled period of the study.

